6.1. Study Stopping Rules

- Death possibly related to the study agent.
- Two patients having a Grade 4 toxicity event that is possibly/probably related to the study agent.

Figure 3A.

[figure not shown]

Figure 3B.

[figure not shown]

Table 3. Calculation of rates of DLT during patient accrual in phase I and phase II

# evaluable for toxicity	Cohort 1 (n=3)	Cohort 2 (n=3)	Cohort 3 (n=6)	Cohort 4 (n=12)	Cohort 5 (n=6)	Cohort 6 (n=10)
# with DLT to be ≥33%	1	2	4	8	10	13

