6. TREATMENT PLAN

Patients will be enrolled into successive dosage level cohorts of 3 or 6 patients and monitored for dose-limiting toxicity (DLT).

DLT (Based on NCI CTCAE version 4.0) is defined as any Grade 2, 3 or 4 immediate hypersensitivity reactions, Grade 3 or 4 fever that may possibly be associated with the immunization, Grade ≥ 2 autoimmune events except for vitiligo or fever for less than 2 days and less than 101.5 °F, Grade ≥ 2 allergic reactions (grade 2 is defined as generalized urticaria as defined by CTCAE version 4.0), or Grade ≥ 3 non-hematologic toxicity.

During dose escalation through the first three patients of cohort 3, there will be a minimum of 1 week between enrolling successive patients. The first patient will be called to check on their condition prior to enrolling the second patient since patients can be enrolled after 1 week of initiation of cohort 3. If no DLT have been observed at this point, then further enrollment can occur in cohort 3 and phase II component (Cohort 4) without the 1-week waiting period. Between dosage levels, through Cohort 3, assessment of DLT for dose escalation will be made after all patients in a cohort have had a study visit at least 3 weeks after receiving their first dose of vaccine and all the available safety data and laboratory results have been reviewed. Patients in cohort 5 may begin injections once all patients in cohort 4 have had at least their first injections and all patients in cohort 3 have had a study visit at least 3 weeks after receiving their first dose of vaccine. If DLT occurs in $<33\%$ of patients in a given dosage level cohort, progression to the next dosage level will proceed. If DLT occurs in $\geq 33\%$ of patients in a given cohort, the next lower dosage level will be defined as the maximum tolerated dose (MTD). If DLT occurs in $<33\%$ of patients in the highest dosage level tested, that dosage level will be defined as the MTD. In phase II (Cohort 4) and Cohort 5, if at any time the rate of DLT in patients enrolled is $\geq 33\%$, the MTD will be re-defined as the next lower dosage level. Additional details of this dose escalation and de-escalation plan are provided below and in Figures 3A, 3B and Table 3.

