- 1) Phase I: Cohort 1: Three patients will receive Ad5 [E1-, E2b-]-CEA(6D) at a dose of 1×10^9 particles in 0.5 mL subcutaneously (SQ) in the same thigh every 3 weeks for 3 immunizations. Immunizations should be separated by 5 cm. A diary card will be given to each subject at the first treatment along with a ruler to record any adverse reactions for 2 days after treatment (24 hours and 48 hours post injection). The diary card will be placed in the study file. Assessment of DLT for dose escalation will be made after all patients in this cohort have had a study visit at least 3 weeks after receiving their first dose of vaccine. If there are no DLT (as defined above), then patients may begin enrolling into cohort 2. If there is 1 DLT then an additional 3 patients will be enrolled at this dosage level. Assessment of DLT for dose escalation will be made after the 3 additional patients have had a study visit at least 3 weeks after receiving their first dose of vaccine. If none of these latter 3 patients have DLT, then patients may begin enrolling into cohort 2. If 2 patients have DLT at this lowest dosage level, dosing will be de-escalated to 1×10^8 particles and a new cohort of 3 patients instituted.
- 2) Cohort 2: Three patients will receive Ad5 [E1-, E2b-]-CEA(6D) at a dose of 1×10^{10} particles in 0.5 mL SQ in the same thigh every 3 weeks for 3 immunizations. Immunizations site should be separated by 5 cm. A diary card will be given to each subject at the first treatment along with a ruler to record any adverse reactions for 2 days after treatment (24 hours and 48 hours post injection). The diary card will be placed in the study file. Assessment of DLT for dose escalation will be made after all patients in this cohort have had a study visit at least 3 weeks after receiving their first dose of vaccine. If there are no DLT, then patients may begin enrolling into cohort 3. If there is 1 DLT then an additional 3 patients will be enrolled at this dosage level. Assessment of DLT for dose escalation will be made after the 3 additional patients have had a study visit at least 3 weeks after receiving their first dose of vaccine. If none of these latter 3 patients have DLT, then patients may begin enrolling into cohort 3. If 2 patients have DLT at this dosage level, the dosage level in cohort 1 will be considered the MTD. If only 3 patients were enrolled in cohort 1, an additional 3 patients will be enrolled at that dosage before proceeding to the next cohort.

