- 3) Cohort 3: Six patients will receive Ad5 [E1-, E2b-]-CEA(6D) at a dose of 1×10^{11} particles in 0.5 mL SQ in the same thigh every 3 weeks for 3 immunizations. Immunizations site should be separated by 5 cm. A diary card will be given to each subject at the first treatment along with a ruler to record any adverse reactions for 2 days after treatment (24 hours and 48 hours post injection). The diary card will be placed in the study file. Assessment of DLT for proceeding to phase II enrollment (Cohort 4) will be made after all patients in this cohort have had a study visit at least 3 weeks after receiving their first dose of vaccine. If there is 0 or 1 DLT, then subjects may enroll in Cohort 4. If 2 patients have DLT at this dosage level, the dosage level in cohort 2 will be considered the MTD. If only 3 patients were enrolled in cohort 2, an additional 3 patients will be enrolled at that dosage before proceeding to the next level.
- 4) Phase II cohort (Cohort 4): After the MTD is established, an additional 12 patients will receive Ad5 [E1-, E2b-]-CEA(6D) at the MTD every 3 weeks for 3 immunizations.

Note: if during accrual of patients in the phase II cohort, DLT occurs at a sufficient rate such that the rate of DLT amongst the total number of patients (those treated at MTD in phase I and those in phase II) is $\geq 33\%$, then phase II will be restarted at the dosage level which is one level below the prior MTD.

- 5) Cohort 5: Six patients will receive Ad5 [E1-, E2b-]-CEA(6D) at a dose of 5×10^{11} particles SQ in 2.5 mL every 3 weeks for 3 immunizations. Assessment of DLT will be made after all patients in this cohort have had all 3 injections and been observed for at least 30 days after the last injection. If there are 0-1 DLT, then this will be declared the maximum feasible dose. If there are 2 or more DLT, then 1×10^{11} particles will be declared the MTD.

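### Table 3's DLT limits are one-third of a running total over all doses, so they contradict the text for cohorts 3 to 5 and cannot occur as printed for cohorts 5 and 6

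*Combined protocol and SAP*

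**What the plan says.** All references are to the latest version in the file, the one that adds cohort 6, unless stated otherwise.

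- Table 3, printed under Section 6.1, heads its columns with single cohorts and their sizes: 3, 3, 6, 12, 6 and 10 for cohorts 1 to 6. The row beneath reads "with DLT to be ≥33% 1 2 4 8 10 13".
- Section 6 makes the table part of the decision plan: "Additional details of this dose escalation and de-escalation plan are provided below and in Figures 3A, 3B and Table 3".
- The general rule in Section 6 works by cohort or dosage level. At 33% or more in a given cohort, the next lower level becomes the MTD. Below 33% "of patients in the highest dosage level tested, that dosage level will be defined as the MTD". The Protocol Summary and Section 8.1 also judge safety by dose level, and Section 8.1 lists the safe counts as 0 of 3, up to 1 of 6, up to 3 of 12 and up to 5 of 18.
- Cohorts 1 and 2 (Section 6, items 1 and 2): "If there is 1 DLT then an additional 3 patients will be enrolled at this dosage level"; two DLTs is the limit.
- Cohort 3 (item 3): "If 2 patients have DLT at this dosage level, the dosage level in cohort 2 will be considered the MTD".
- Cohort 4 has two statements. The item 4 Note uses "the rate of DLT amongst the total number of patients (those treated at MTD in phase I and those in phase II"), that is, 6 + 12 = 18 patients at one dose. The general text says "In phase II (Cohort 4) and Cohort 5, if at any time the rate of DLT in patients enrolled is" 33% or more, without mentioning phase I patients.
- Cohort 5 (item 5): "If there are 0-1 DLT, then this will be declared the maximum feasible dose"; two or more make 1×10^11 the MTD.
- Cohort 6 (item 6): up to ten patients at 5×10^11, the cohort 5 dose. No DLT count is given.

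**The concern.** A row labelled as the number of DLTs that reaches 33% should hold, under each column, the smallest count that is at least 33% of the patients being judged. Here two entries exceed the number of patients in their own column, and three others are two-thirds of it.

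The table is not decorative, because Section 6 names it as a source of the escalation and de-escalation limits, and safety is the primary objective. A user who took the limits from Table 3 would accept 3 DLTs of 6 in cohort 3, or any number in cohort 5, where the text lowers the MTD at 2. For cohort 6 there is no item-level count to correct the table. Many DLTs in this protocol, such as a Grade 3 non-hematologic toxicity or a Grade 2 autoimmune event, would trigger neither the Grade 4 rules nor the death rules.

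**Working it through.** **Inputs.** Column sizes and limits come from Table 3. Text limits come from Section 6 items 1 to 6, the general paragraph of Section 6, and Section 8.1. Printed cohort sizes are used.

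**Reproducing the printed row.** Sum the column sizes, then divide by 3. The last two columns show the smallest count that is at least 33% of the cohort's own size, and the text's limit.

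| Cohort | n | Running total | Total / 3 | Table 3 | Table 3 / n | ≥33% of own n | Text |
|---|---|---|---|---|---|---|---|
| 1 | 3 | 3 | 1 | 1 | 33% | 1 | 1 of 3 expands, 2 of 6 is the limit |
| 2 | 3 | 6 | 2 | 2 | 67% | 1 | 1 of 3 expands, 2 of 6 is the limit |
| 3 | 6 | 12 | 4 | 4 | 67% | 2 | 2 of 6 |
| 4 | 12 | 24 | 8 | 8 | 67% | 4 | 6 of 18 (Note), or 4 of 12 |
| 5 | 6 | 30 | 10 | 10 | 167% | 2 | 2 of 6 |
| 6 | 10 | 40 | 13.3 | 13 | 130% | 4 | no count in item 6 |

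The running total reproduces all six entries, with the last rounded down. Own-cohort sizes reproduce only the first.

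**The last entry on its own basis.** 13/40 = 32.5%, which is below 33%; 14/40 = 35%. The count should be 14.

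**Cohorts 1 and 2.** Cohort 1's 1 agrees with the text. Cohort 2's 2 equals the text's limit after expansion to 6. Neither is claimed as a conflict.

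**Cohort 6 under the general rules.** The given-cohort sentence in Section 6 implies 0.33 × 10 = 3.3, so 4 of 10. The dose-level wording in the Protocol Summary and Section 8.1 would add cohort 5's six patients at the same dose: 0.33 × 16 = 5.28, so 6 of 16. Section 8.1 lists a count for neither 10 nor 16.

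**Reading 13 as pooled over all doses.** Suppose every earlier cohort passed its text rule without expansion. Earlier DLTs are then at most 0 + 0 + 5 + 1 = 6 (cohort 1, cohort 2, cohorts 3 and 4 together, cohort 5). Reaching 13 needs at least 13 − 6 = 7 of 10 in cohort 6. With 2 or fewer earlier DLTs it needs at least 11 of 10, which is impossible.

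**Size of the denominator questions.** The cohort 4 rule applies throughout accrual, so it is checked after each patient, with the smallest count that is at least 33% of the patients so far. Conditioning on 0 or 1 DLT of 6 in cohort 3, at true DLT rates of 20% / 30%, cohort 4 judged alone triggers with probability 0.58 / 0.79. Judged with cohort 3 it triggers with 0.13 / 0.36. The same check applied to cohort 6 at an illustrative 40% rate gives 0.90 alone, against 0.31 or 0.62 with cohort 5 included (0 or 1 DLT there). The figures for a cohort judged alone are high partly because a single DLT among the first three patients already reaches 33%.

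**The case against.** The strongest reply is that the table changes little in practice. The items in Section 6 give usable limits for cohorts 1 to 5. The preceding version's Protocol Summary already names 1×10^11 as the MTD, so the columns for cohorts 1 to 3 look historical. Both points stand, and they limit the harm there to an inconsistent reference table.

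A reader might infer that cohort 6 has no DLT limit, or that its patients are unprotected. The documents do not support that. The general 33% rule in Section 6 still applies, and its given-cohort sentence points to 4 of 10. A related DLT ends that patient's treatment (Section 7.3.4.2). The investigator or sponsor may suspend vaccinations, and the Grade 4 and death rules in Sections 6 and 6.1 remain. What survives is narrower: none of these says whether cohort 5 counts, and the one count printed for cohort 6 is wrong.

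It could also be said that a running total was intended. Section 6 does describe a cumulative review over all participants, but only for the halting rules on Grade 4 allergic reactions and on deaths. The Note to item 4 pools phase I and phase II patients only at the MTD. Even a deliberate running total would need 14 in the last column.

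Figures 3A and 3B are not available and may carry a cohort 6 rule. They could not make the Table 3 row correct.

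**Conclusion.** Table 3 is wrong as written. Its limits come from one-third of a running total over all doses, a basis found in none of the text's 33% rules. They conflict with the text for cohort 3 (4 against 2 of 6), cohort 4 (8 against 6 of 18, or 4 of 12 if the general sentence means cohort 4 alone) and cohort 5 (10 against 2 of 6). The entries for cohorts 5 and 6 exceed the cohort sizes printed above them.

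For cohorts 1 to 5 this is a documentation error, since explicit text is available. The live consequence is cohort 6: its only specific count is 13 of 10, while the general wording supports two different limits, 4 of 10 or 6 of 16. It would go too far to conclude that unsafe escalation was permitted or that cohort 6 lacked a safety rule.

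The arithmetic rests on the printed cohort sizes and ignores replacements and expansions. The probabilities also assume independent patients and the stated illustrative rates, and they show only that the choice of denominator matters. The correction should be made.

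**What to change.** Replace Table 3 with decision limits by dosage level that match the text:

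- **1×10^9 and 1×10^10:** 1 of 3 expands the cohort; 2 of 6 is the limit.
- **1×10^11:** 2 of 6 in cohort 3; then, during accrual of cohort 4, 33% or more of cohorts 3 and 4 combined (6 of 18 at full accrual).
- **5×10^11:** 2 of 6 in cohort 5; then one stated denominator for cohort 6, either 4 of 10 alone or 6 of 16 with cohort 5.

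State that the limit at any time within cohorts 3 and 5 is 2 DLTs. Otherwise one DLT among the first three patients would reach 33% and clash with the allowance of 0 or 1 of 6 in items 3 and 5.

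Amend the phase II sentence in Section 6 so that cohort 4's rate is taken among patients at the MTD, phase I and phase II together, and give cohort 5 its own sentence. The restriction to the MTD must be included: combining phase I and phase II without it would pool 3 + 3 + 6 + 12 = 24 patients and bring back the limit of 8.

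The cost is one table and a few sentences in an amendment, with no extra patients or procedures.

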6.2. Pharmaceutical Information

6.2.1 Dosage and Administration

Patients will receive Ad5 [E1-, E2b-]-CEA(6D) at a dose of 1×10^9 , 1×10^{10} , or 1×10^{11} virus particles (vp) per immunization in 0.5 mL of sterile saline SQ every 3 weeks for 3 immunizations. The 5th cohort will receive Ad5 [E1-, E2B-]-CEA(6D) at a dose of 5×10^{11} virus particles (vp) per immunization in 2.5 mL of sterile saline SQ every 3 weeks for 3 immunizations. The 6th cohort will receive Ad5 [E1-, E2B-]-CEA(6D) at a dose of 5×10^{11} virus particles (vp) per

immunization in 1.0 mL SQ every 3 weeks for 3 immunizations and each additional boost will be delivered at the same dose.

6.2.2 How Supplied

ETBX-011 will be provided in a frozen state in a 2ml vial with a fill volume of 0.5 ml of extractable vaccine which contains 1×10^{11} total virus particles. The volume of injection for 1×10^{11} virus particles is 0.5 mL. The lower doses will be produced by dilution in 0.9% saline using the following directions. For cohort 6, ETBX-011 will be provided in a frozen state in a 2ml vial with a fill volume of 1.0 ml of extractable vaccine which contains 5×10^{11} total virus particles. The volume of injection for 5×10^{11} virus particles is 1.0 mL. The product should be stored at -20°C until used.

Instructions for dose preparation:

Cohort 1: To administer 1×10^9 virus particles by subcutaneous injection, perform 2 serial dilutions of vial vaccine as follows:

1. Draw 4.5 mL of sterile saline into a syringe.
2. Using a second syringe, withdraw 0.5 mL of previously thawed ETBX-011 from the supplied vial.
3. Remove the needle from syringe containing the 4.5 mL saline, and inject the 0.5 mL of ETBX-011 from the second syringe into the syringe containing saline.
4. Mix. This new solution has a concentration **2×10^{10} vp/mL**.
5. Use a new sterile syringe with a needle and repeat above procedure.
6. Withdraw 4.5 mL of sterile saline.
7. In the second syringe withdraw 0.5 mL from the syringe containing **2×10^{10} vp/mL**.
8. Remove the needle from the syringe containing the 4.5 mL saline, and inject the 0.5 mL of 2×10^{10} vp/mL from the second syringe.
9. Place a new needle on the 10-mL syringe from Step 8 above and mix the two solutions. This solution now has a concentration **2×10^9 vp/mL** (1×10^9 vp per 0.5 mL).
10. Label a new 1-mL sterile syringe ETBX-011, 1×10^9 vp and withdraw 0.5 mL from the syringe containing **2×10^9 vp/mL**. This prepared vaccine (**ETBX-011, 1×10^9 vp**) can be kept at room temperature for four hours prior to administering to the patient.

Cohort 2: To administer 1×10^{10} virus particles by subcutaneous injection:

1. Draw 4.5 mL of sterile saline into a syringe.
2. Using a second syringe, withdraw 0.5 mL of previously thawed ETBX-011 from the supplied vial.
3. Remove the needle from syringe containing the 4.5 mL saline, and inject the 0.5 mL of ETBX-011 from the second syringe into the syringe containing saline.
4. Mix. This new solution has a concentration **2×10^{10} vp/mL**.
5. Label a new 1-mL sterile syringe ETBX-011, 1×10^{10} vp and withdraw 0.5 mL from the syringe containing **2×10^{10} vp/mL**. This prepared vaccine (**ETBX-011, 1×10^{10} vp**) can be kept at room temperature for four hours prior to administering to the patient.

Cohort 3 and 4: To administer 1×10^{11} virus particles by subcutaneous injection:

1. Withdraw 0.5mL of contents from the previously thawed, supplied ETBX-011 from the vial and administer to each subject without any further manipulation.

Cohort 5: To administer 5×10^{11} virus particles by subcutaneous injection:

1. Withdraw 0.5mL of contents from each of 5 previously thawed ETBX-011 vials (total volume 2.5ml) and administer to each subject without any further manipulation.

Cohort 6: To administer 5×10^{11} virus particles by subcutaneous injection:

1. Withdraw 1.0mL of contents from the previously thawed, supplied ETBX-011 from the vial and administer to each subject without any further manipulation.

6.2.3 Disposal of Unused Vaccine

Unless other arrangements are agreed in writing, all unused vaccine should be delivered to [name], at Etubics Corporation for disposal at or before the completion of the clinical study.

7. TREATMENT EVALUATION

7.1. Short-Term Evaluation During and After Active Immunotherapy

On vaccine administration days, blood will be drawn before administration. Evaluations will also be conducted for patients who discontinue from the study if they have received any treatment. The investigator will determine the degree of evaluation based on the patient's condition and/or reason for discontinuation from the study.

7.1.1 General Evaluations

Weeks 0, 3, 6 (Immunization Visits):

General evaluations include medical history, Karnofsky performance status, and complete physical examination with weight by the attending physician. Any other treatments, medications, biologics, or blood products that the patient is receiving or has received since the last visit will be recorded. Patients will remain in the clinic for approximately 30 minutes following receipt of vaccine to monitor for any adverse reactions. Local and systemic reactogenicity after each dose of vaccine will be assessed daily for 3 days (on the day of immunization and 2 days thereafter) using diary cards to report symptoms and a ruler to measure local reactogenicity.

Week 9:

General evaluations include medical history, Karnofsky performance status, and complete physical examination with weight by attending physician. Any other treatments, medications, biologics, or blood products that the patient is receiving or has received since the last visit will be recorded. Immunization injection sites will be assessed.

7.1.2 Hematological and Biochemical Assessment

Weeks 0, 3, 6 (Immunization Visits):

Blood will be drawn to perform chemistry and hematology, including CBC with differential, Na, K, Cl, CO₂, BUN, creatinine, Ca, total protein, albumin, total bilirubin, alkaline phosphatase, AST, ALT and glucose.

Week 9:

Blood will be drawn to perform chemistry and hematology, including CBC with differential, Na, K, Cl, CO₂, BUN, creatinine, Ca, total protein, albumin, total bilirubin, alkaline phosphatase, AST, ALT, glucose and ANA.

7.1.3 Biological Markers

Weeks 0 and 9:

Serum (5ml) to measure antibodies to CEA and the Ad5 vector will be obtained and sent to Etubics Corporation for determination. Biomarkers (e.g., CEA or CA15-3) will be reviewed if determined and available.

7.1.4 Immunological Assessment

Weeks 0, 3, 6, and 9:

Peripheral blood (90mL) will be drawn prior to each immunization and approximately 3 weeks after the last immunization to determine whether there is an effect on the immune response at specific time points during the study and/or after a specific number of immunizations. Peripheral blood mononuclear cells (PBMC) will be assayed for T cell responses to CEA using ELISPOT at all time points, plus proliferation assays, multi-parameter flow cytometric analysis, and cytotoxicity assays, if possible and at the discretion of the investigator. Serum from each blood draw will be archived and sent to Etubics Corporation for Ad5 neutralizing level determination.

7.2. Long-Term Follow-Up

Patients will be requested to continue long-term follow-up every 3 months for 1 year. At each visit, a medical history and physical exam and the following lab tests will be performed: blood chemistry and hematology, including CBC with differential, Na, K, Cl, CO₂, BUN, creatinine, Ca, total protein, albumin, total bilirubin, alkaline phosphatase, AST, ALT and glucose.

At each visit, 40-90 mL of peripheral blood should be drawn for immune analysis, if there was previous evidence of an immune response or at the discretion of the investigator. Available serum markers (e.g., CEA, CA15-3) will be reviewed.

